## **2.2 Potential Risks and Benefits**

### **2.2.1 Potential Risks**

Cetuximab-related risks include infusion reactions, acneiform rash, and in rare cases cardiopulmonary arrest and or interstitial lung disease (see details in section 6.2.1.) Other risks include those related to the research biopsy (bleeding and infection at the site where the needle is inserted, brief pain during the procedure) and blood draws (bruising, swelling at the injection site, dizziness and lightheadedness), as well as loss of confidentiality. Other study-related procedures that may introduce “risks” to study participants include:

- 1) Urine/serum pregnancy tests;
- 2) Premedication with diphenhydramine/acetaminophen prior to Cetuximab infusions;
- 3) Potential medications used to treat Cetuximab-related rashes (Hydrocortisone, Doxycycline, Clindamycin);
- 4) Risks of developing and/or correction of electrolyte disturbances due to Cetuximab infusion

## 2.2.2 Potential Benefits

There may be clinical benefit to the two administrations of cetuximab prior to surgery. Preliminary preclinical data suggest a role for AXL in cetuximab resistance in head and neck squamous cell carcinoma. AXL may potentially serve as a functional biomarker for cetuximab response in humans. Targeting AXL has the potential to resensitize tumors to cetuximab therapy. Treatment with two doses of cetuximab may offer clinical benefit including decreasing the tumor volume of the cancer to allow for easier resection at the time of surgery. Other benefits may include a predictive response that may determine sensitivity of a patient's cancer to systemic treatment.

## 3 OBJECTIVES

### 3.1 Study Objectives

**Primary:** To evaluate the hypothesis that low AXL correlates with clinical response to cetuximab in head and neck cancer patients

**Secondary:** To further describe the safety of pre-operative administration of cetuximab

**Correlative:**

1. To correlate AXL expression with change in Ki67 following cetuximab in HNC patients
2. To examine other putative markers of cetuximab sensitivity such as HER3 and change in circulating tumor cells and other biomarkers
3. To establish the first panel of patient-derived xenografts from patients with known sensitivity or resistance to cetuximab

### 3.2 Study Outcome Measures

#### 3.2.1 Primary Endpoint

*The objective response rate (ORR) measured by clinical examination and clinical measurements at the time of diagnosis and within 48 hours prior to surgery*

This objective is to compare levels of AXL prior to CTX treatment to the clinical response and changes in the size of the primary tumor mass or lymph nodes. Patients will have their squamous cell carcinoma (either primary site or nodal metastases) measured in centimeters by the clinical

team via clinical measurement at two timepoints: 1) the time of diagnosis (pre- CTX) and 2) after treatment with 2 doses of cetuximab and within 48 hours prior to surgery (post-CTX).

### **3.2.2 Secondary Endpoint**

*The rate of hospital re-admissions for wound care or surgical complications attributed to cetuximab (such as fistula or deep cellulitis) within 28 days after surgery*

Although the use of cetuximab pre-operatively has been studied in a pre-operative trial, this clinical trial will expand upon this information to further evaluate any other complications during surgery due to pre-operative cetuximab. We will also plan a descriptive analysis of all AEs and SAEs associated with pre-operative cetuximab.

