### **9.1.3 *Serious Adverse Events***

A serious adverse event (SAE) is one that meets one or more of the following criteria:

- Results in death
- Is life-threatening (places the subject at immediate risk of death from the event as it occurred)

- Results in inpatient hospitalization or prolongation of existing hospitalization
- Results in a persistent or significant disability or incapacity
- Results in a congenital anomaly or birth defect
- An important medical event that may not result in death, be life threatening, or require hospitalization may be considered an SAE when, based upon appropriate medical judgment, the event may jeopardize the subject and may require medical or surgical intervention to prevent one of the outcomes listed in this definition.

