### **Procedures for Recording and Reporting Serious Adverse Events**

- SAEs will be reported from time of informed consent until 28 days after discontinuation of cetuximab or definitive surgery, whichever is later.
- Any SAEs experienced after this 28-day period will only be reported if the investigator suspects a causal relationship (possibly, probably or definitely related) to the study treatment.
- SAEs will be reported on the SAE Submission Form and entered in SAE tab in OnCore within 1 business day of discovery of the event.
- SAEs include events related and unrelated to the study drug(s).
- SAEs will be recorded in the subject's medical record and on the appropriate study specific eCRF form within OnCore.
- All SAEs, regardless of relation to study drug, will be followed until resolution to ≤ Grade 1 or baseline and/or deemed clinically insignificant and/or until a new anti-cancer treatment starts, whichever occurs first.
- Recurrent episodes, complications, or progression of the initial SAE will be reported as follow-up to the original episode within 24 hours of the investigator receiving the follow-up information.

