#### **Analysis of Secondary Endpoints**

The safety of pre-operative cetuximab, as evaluated by hospital re-admissions for wound care or surgical complications attributed to cetuximab within 28 days after surgery, will be reported as a proportion including an exact 95% confidence interval.

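### The only pre-specified safety proportion counts re-admissions, so a serious complication or death before first discharge cannot enter it

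*Combined protocol and SAP*

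**What the plan says.** The secondary objective (Section 3.1) is to describe further the safety of giving cetuximab before surgery. Section 3.2.2 turns this into one endpoint, "The rate of hospital re-admissions for wound care or surgical complications attributed to cetuximab", with the qualifier "such as fistula or deep cellulitis) within 28 days after surgery". The text beneath it says the trial will expand on an earlier study "to further evaluate any other complications during surgery due to pre-operative cetuximab", and it plans a descriptive analysis of AEs and SAEs.

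Section 12.4 repeats the definition, taking safety "as evaluated by hospital re-admissions for wound care or surgical complications attributed to cetuximab within 28 days after surgery". Its only instruction for the analysis of that quantity is that it "will be reported as a proportion including an exact 95% confidence interval". No other safety quantity has a pre-specified estimate and interval. Section 12.2 sets the safety population as everyone who has a research biopsy.

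Post-operative events are also collected elsewhere:

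- Section 4 has readmission, wound healing and infection assessed at one month, give or take two weeks, with complications graded on a five-level scale of relationship to cetuximab.
- Section 9.1.3 counts as serious any event that causes death, is an important medical event, or meets the criterion "Results in inpatient hospitalization or prolongation of existing hospitalization".
- Sections 9.2 and 9.4 record SAEs, related or not, to at least 28 days after surgery. Recording of other AEs ends no later than the day of surgery.

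**The concern.** Re-admission presupposes discharge. Complications that arise while the patient is still in hospital after the resection, including any that prevent discharge or cause death, fall outside the event by construction. Yet the objective is peri-operative safety, and the endpoint's own examples (fistula, deep cellulitis) can arise before discharge as well as after it.

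The proportion and its interval are the one quantified safety result. If most serious complications occur during the first stay, that result could be low or zero while the SAE listing shows several events. Two further features affect the same figure: which events count as attributed to cetuximab, and who is in the denominator.

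**Working it through.** The plan states no expected rate, threshold or precision for this endpoint, so there is no figure of its own to reproduce. The planned 36 patients are powered on tumour response (Section 12.2) and serve here only as a sample size.

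**1. Which events can enter the numerator**

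| Event within 28 days of surgery | In the 12.4 proportion? | Recorded elsewhere? |
|---|---|---|
| Re-admission for a wound or surgical complication | Yes, subject to attribution | SAE; one-month assessment |
| Serious complication before first discharge | No | SAE if it prolongs the stay, is life-threatening or is an important medical event |
| Death before first discharge | No | SAE |
| Non-serious wound problem before first discharge | No | Outside AE recording; the one-month assessment may show it |

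No rule says how to score a patient who dies in hospital or is still an inpatient at day 28.

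**2. Attribution**

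In "hospital re-admissions for wound care or surgical complications attributed to cetuximab within 28 days after surgery", the words about attribution can govern the whole phrase or only the surgical complications. On the second reading a wound-care re-admission counts whatever its cause. Neither 3.2.2 nor 12.4 names the level of the Section 4 scale at which an event is attributed. Section 9.3.1 groups possible, probable and definite as related, while the halting rule in Section 9.5 uses probably related. The endpoint refers to neither.

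**3. Size, on assumed counts**

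Intervals are exact (Clopper-Pearson) 95% limits. Suppose 5 of 36 operated patients have a qualifying complication, 4 of them only during the first stay.

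- Endpoint as written: 1/36 = 2.8% (0.1% to 14.5%).
- All five counted: 5/36 = 13.9% (4.7% to 29.5%).
- If all five fell in the first stay: 0/36 = 0% (0% to 9.7%).

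More generally, let q be the true complication rate and f the share confined to the first stay. The expected number of patients with a complication is 36q, and the expected number counted is 36q(1 − f). The chance of reporting none is (1 − q(1 − f))^36.

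| q | f | Expected | Counted | P(report 0) | P(0) if all counted |
|---|---|---|---|---|---|
| 10% | 25% | 3.6 | 2.7 | 6.0% | 2.3% |
| 10% | 75% | 3.6 | 0.9 | 40% | 2.3% |
| 20% | 50% | 7.2 | 3.6 | 2.3% | 0.03% |
| 30% | 25% | 10.8 | 8.1 | 0.01% | under 0.01% |
| 30% | 75% | 10.8 | 2.7 | 6.0% | under 0.01% |

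These rows assume that every counted event passes the attribution test. A stricter cut-off lowers the counted column further.

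**4. Denominator**

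Registration has two steps (Section 5.1). The research biopsy belongs to Step 1 and cetuximab to Step 2, so a biopsied participant who fails Step 2 stays in the safety population but cannot have the event. Section 5 expects about 100 people to be screened. In the extreme case that all were biopsied, zero events would give an upper limit of 3.6% (0/100) instead of 9.7% (0/36), and five events would read as 5.0% (1.6% to 11.3%) instead of 13.9%. The true denominator lies somewhere between.

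**The case against.** The strongest reply is that a re-admission rate is a legitimate descriptive endpoint and that safety reporting does not depend on it. Deaths, prolonged stays and important medical events are recorded as SAEs regardless of relationship to at least 28 days after surgery, reported to the funder, and described in the analysis. Probably related SAEs feed the halting rule in Section 9.5. Section 4 also assesses wound healing and infection, not only readmission. The objective is descriptive, with no hypothesis or threshold. This all stands, and it limits the point to what the quantified result represents.

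A reader might infer four stronger things that the documents do not support:

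- **That in-hospital complications go unreported.** They are missing from one proportion, not from the SAE data.
- **That Section 3.2.2 contradicts itself by mentioning complications during surgery.** That sentence describes the trial rather than the endpoint, and is itself limited to complications due to cetuximab.
- **That the estimate is biased.** A re-admission proportion estimates re-admissions correctly. The shortfall is against the safety objective.
- **That only attributed re-admissions count, or that a patient still in hospital at day 28 is scored event-free.** The wording is ambiguous on the first, and there is no rule on the second.

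It is also fair to say that an all-cause complication rate in a single-arm trial cannot separate cetuximab's contribution from that of surgery. That is a reason to report both figures, not to leave first-stay events out of both.

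**Conclusion.** The point holds as a gap between objective and endpoint, and it is a cheap improvement rather than an error in a stated figure. On the natural reading of Sections 3.2.2 and 12.4, no complication or death before first discharge can enter the only safety proportion with an interval. The proportion can therefore understate peri-operative complications. The open attribution rule leaves the numerator partly undefined, and the biopsy-based population can dilute the rate further.

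The size is unknown, because the documents give neither a complication rate nor the share arising in hospital. Over the assumed range (10% to 30% true rate, 25% to 75% confined to the first stay, 36 patients), 0.9 to 8.1 patients would be counted out of 3.6 to 10.8. The primary analysis is unaffected.

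**What to change.** In Sections 3.2.2 and 12.4:

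1. Keep the re-admission rate as a component, and state whether the attribution condition applies to wound-care re-admissions.
2. Add the proportion, with exact 95% interval, of participants who have any wound or surgical complication from surgery to day 28 that meets an SAE criterion already recorded: death, prolonged index hospitalisation, re-admission, or important medical event (which can include reoperation).
3. Report it (a) regardless of attribution and (b) for events at or above a named level of the Section 4 scale.
4. Use as denominator the participants who received at least one cetuximab dose and had surgery. The biopsy-based population can remain for the general AE description.
5. State what counts as prolonged hospitalisation. Section 9.1.3 sets no minimum duration, while Table 1 in Section 9.4 refers to at least 24 hours.

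The cost is mainly wording, since the SAE data are already collected through day 28. Counting every unplanned return to theatre separately would need one CRF field. The reported rate will be higher, and the all-cause figure cannot isolate cetuximab's contribution without a comparator; the report should say so. No dose, visit or sample size changes.

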### **3.2.3 Exploratory Endpoints**

- 3.2.3.1 Change in Ki67 from pre- versus post-cetuximab treated tumors and its correlation with levels of AXL expression pre-cetuximab treatment
- 3.2.3.2 Correlation of measures of putative markers of cetuximab sensitivity, including protein, RNA, circulating tumor cells with cetuximab response, measured by Ki67
- 3.2.3.3 Establishment of patient-derived xenografts with known sensitivity/resistance to cetuximab

## **4 STUDY DESIGN**

This clinical trial is a single-site, single arm, open label, window of opportunity study for patients with squamous cell carcinoma of the head and neck. Subjects (targeted N=36) are patients who have biopsy-proven, squamous cell carcinoma of the head and neck, excluding advanced cutaneous head and neck squamous cell carcinoma, who are anticipated to undergo surgical resection of the tumor, and who are candidates for cetuximab pre-operative therapy. Patients with newly diagnosed cancer or those who present with recurrent disease are eligible for this trial. All patients will undergo a research biopsy (in clinic or at the time of panendoscopy—not standard of care) and a staging workup with cross-sectional imaging of the neck (standard of care).

### Research-related Biopsies and Blood Draws

Research-related procedures include a separate research biopsy of the tumor at the time of the diagnostic biopsy for analysis of Ki67, putative markers of CTX sensitivity, and research-related blood draws for collection of circulating tumor cells at five timepoints: screening visit, within 24 hours prior to surgery, and at follow-up visits: approximately 1 month post-surgery, as well as approximately 3 and 12 months post definitive care. The tissue obtained for research biopsy will be placed in culture media or saline and provided to the biologic correlate study team. If pathology confirms a diagnosis other than HNSCC, the patient will be removed from the study, and the research biopsy tissue will be released to the University of Wisconsin Translational Science BioCore (TSB) Biobank. If the clinical biopsy is inconclusive, the research tissue will be released back to University of Wisconsin Surgical Pathology department to aid in a clinical diagnosis. The research-related blood draws will be given directly to the biologic correlate study team for quantification of circulating tumor cells and/or other biomarkers.

### Cetuximab Administration in the Pre-operative Setting

Cetuximab is an FDA approved chemotherapy agent for the treatment of (a) locally or regionally advanced squamous cell carcinoma of the head and neck in combination with radiation therapy, (b) recurrent locoregional disease or metastatic squamous cell carcinoma of the head and neck in combination with platinum-based therapy with 5-FU, and (c) recurrent or metastatic squamous cell carcinoma of the head and neck progressing after platinum-based therapy. Treatment with cetuximab prior to surgical resection is considered the investigational portion of this study, as neoadjuvant cetuximab is not considered standard of care. However, treatment with cetuximab as a monotherapy may offer a benefit to patients as cetuximab is a known and approved chemotherapy agent for the treatment of head and neck cancer. In patients with recurrent and/or metastatic HNSCC with progression on platinum-based chemotherapy, those patients who were treated with cetuximab monotherapy had overall response rates from 10-13% and disease control rates from 46-56%. Although surgical resection will offer definitive treatment for local HNSCC, use of neoadjuvant cetuximab may offer disease response such as shrinkage of the tumor that may offer improved surgical resection.

Cetuximab will be given twice via IV infusions at pre-specified doses within a 14-day period between the time of their biopsy confirming their cancer and their scheduled surgery. Given that the standard of care time interval between diagnosis/consult and curative surgical resection is approximately 4-6 weeks at the University of Wisconsin, treatment with pre-operative cetuximab is not anticipated to delay curative surgical resection. No dose reductions of cetuximab are allowed although the rate of infusion of the drug can be reduced at the discretion of the investigator as per the standard of care infusion rate modifications noted in the FDA prescribing information of cetuximab.

### Surgical Resection

The surgical resection is considered standard of care therapy for this study population. Patients will undergo definitive standard of care surgery within 4 weeks of the first protocol dose of cetuximab.

Specimens from the tumor resection will be transferred to pathology in culture media or saline per standard operating procedures. The biologic correlate study team will wait for the pathology team to access the specimen in the gross room and then will be given a portion of tissue that will not be required for diagnosis (i.e., remnant). The study team will then process and embed that fresh tissue to an FFPE block for downstream studies. Alternatively, the biologic correlate study team will request 20 x 5  $\mu$ m unstained FFPE slides from the diagnostic tissue after surgical pathology clinical review is complete.

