### Schematic of Study Design:

The primary objective of this window of opportunity study is to test the hypothesis that low AXL expression correlates with clinical response to cetuximab in head and neck cancer patients. The secondary objective of this study is to further describe the safety of pre-operative administration of cetuximab. It is estimated that from the time of diagnosis/consult to resection of tumor is approximately 4-6 weeks. There is no absolute timeframe for study procedures to occur, although all protocol activities must be completed prior to resection.

This is a window of opportunity trial to study AXL and CTX in HNSCC patients. HNSCC patients who will undergo surgery will be identified. The tumor will be measured by the treating physician. A research biopsy will be taken and scored for Ki67 and proteins hypothesized to be involved in CTX resistance, such as AXL, EGFR and HER3. A section of the biopsy will be used for PDX development. A blood draw will be taken for circulating tumor cell analysis. Patients will receive two doses of cetuximab. Safety will be evaluated and blood will be collected for quantification of circulating tumor cells prior to resection. Remnant tissue from the resected tumor will be stained for Ki67 and compared to pre-treatment tumors. It will also be analyzed for proteins hypothesized to be involved in CTX resistance, such as AXL, EGFR and HER3. Patients will have blood draws for circulating tumor cells at 3 follow up timepoints: one month post-surgery, 3 months post definitive care and 12 months post definitive care. Patients will then continue on to standard of care.

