### **6.3 Modification of Study Product Administration for a Subject**

#### **Dose Delays/Dose Modifications**

- No dose modifications will be planned. Please refer to section 6.2.1 (subsection, Infusion Reactions) for more information regarding infusion rate decreases in the setting of infusion reaction.
- Dose delays secondary to intolerance (such as infusion reactions) are permitted. Subjects can be rechallenged with cetuximab within 3 days but will otherwise be discontinued from the study.
- Expected adverse events that would delay cetuximab infusion:
  - Grade 3 or higher nausea, vomiting, diarrhea, stomatitis, or rash uncontrolled despite maximal medical management due to a toxicity that is considered at least PROBABLY related to study treatment
  - Any other Grade 3 or higher non-hematologic toxicity, except grade 3 fatigue lasting >7 days, due to a toxicity that is considered at least PROBABLY related to study treatment
  - Grade 3 or 4 electrolyte abnormalities that are corrected within 48 hours will not be considered a serious adverse event.

---

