### Study Visit 4, Cetuximab Dose 2 (7 days +/- 3 days from Study Visit 3)

- Vital signs (blood pressure only) (recorded for the study from medical records maintained as part of standard clinical care for CTX administration)
- Blood Chemistry: Potassium, calcium and magnesium (recorded for the study from medical records maintained as part of standard clinical care for CTX administration)
- Adverse event evaluation (standard clinical care for CTX administration)
- Administration of cetuximab (research-related)

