### Study Visit 5, Safety Evaluation (within 7 days prior to surgery)

- Concomitant medications (recorded for the study from medical records maintained as part of standard clinical care for CTX administration)
- Physical exam (recorded for the study from medical records maintained as part of standard clinical care for CTX administration)
- Vital signs (blood pressure, heart rate, temperature) (recorded for the study from medical records maintained as part of standard clinical care for CTX administration)
- Weight (recorded for the study from medical records maintained as part of standard clinical care for CTX administration)

- ECOG performance status (recorded for the study from medical records maintained as part of standard clinical care for CTX administration)
- CBC with differential (recorded for the study from medical records maintained as part of standard clinical care for CTX administration)
- Blood chemistries (chloride, bicarbonate, BUN creatinine, glucose, AST, ALT, Alk Phos, T. bili, calcium, magnesium, T. protein and albumin) (recorded for the study from medical records maintained as part of standard clinical care for CTX administration)
- Adverse event evaluation (standard clinical care for CTX administration)
- Measurement of tumor size via clinical assessment (research-related)

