### **Determination of putative biomarkers of CTX sensitivity**

The biologic correlate study team will formalin fix and paraffin embed (FFPE) approximately one third of the research biopsy tissue to be used to assess putative biomarkers of CTX sensitivity (e.g. total and phosphorylated AXL, EGFR and HER3 expression using immunohistochemistry assays). The FFPE research and surgical specimens will be used to establish the change in Ki67 ( $\Delta$ Ki67).

Correlations between the change in Ki67 index ( $\Delta$ Ki67) and AXL expression and HER3 expression in the research biopsy will be performed. Further correlation between other biomarkers and AXL expression will be performed.

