#### **Analysis of Correlative Endpoints**

Summary statistics of the change in Ki67 ( $\Delta$ Ki67), as established by the surgical specimen, will be reported for the response to cetuximab endpoint. Correlation between  $\Delta$ Ki67 and putative biomarkers will be analyzed as a continuous variable and will be tested using Pearson's correlation coefficient. Correlation between two biomarkers such as AXL and HER3 expression as continuous variables will be investigated using Pearson's correlation coefficient.

Summary statistics will be used to report circulating tumor cells at each time point and the changes between time points. The association of change in circulating tumor cells with  $\Delta$ Ki67 (early response) will be explored graphically and with Pearson's correlation coefficient.

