### FOOTNOTES

1. Pre-study tests to be done within 21 days of dose 1 cetuximab therapy.

2. Time between doses: 7 days (+/-3 days)
3. Informed consent to be obtained within 28 days of starting treatment.
4. If screening/baseline procedures are within 7 days prior to cetuximab dose 1, they don't need to be repeated on day of dose 1.
5. Serum chemistry should include: sodium, potassium, chloride, bicarbonate, BUN, creatinine, glucose, AST, ALT, alkaline phosphatase, total bilirubin, calcium, magnesium, protein, albumin.
6. A negative serum/urine pregnancy test is required within 7 days prior to cetuximab dose 1.
7. For subjects with unresolved treatment-related toxicity, follow as medically appropriate until resolution or stabilization.
8. Pre-surgical blood draw for circulating tumor cells in serum should be done within 1 day prior to surgery.
9. Prior to dose 2, required labs: magnesium, calcium and potassium
10. Definitive therapy is defined as surgery alone, surgery + XRT or Surgery + chemoXRT
11. Within 7 days prior to surgery, but as close as possible to surgery.
12. May include any of the SOC imaging such as PET/CT, PET/MRI, CT or MRI
13. Blood Pressure only

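### The interval from dose 2 to the resection that supplies post-treatment Ki67 may run from about 1 to 24 days, and the exploratory Ki67 correlations in Section 12.4 take no account of it

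*Combined protocol and SAP*

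**What the plan says.** **Timing.** Section 4 (Surgical Resection) sets the only limit on surgery: "Patients will undergo definitive standard of care surgery within 4 weeks of the first protocol dose of cetuximab". Appendix A, footnote 2, gives "Time between doses: 7 days (+/-3 days"), and Section 7.2 repeats it in the visit heading "Study Visit 4, Cetuximab Dose 2 (7 days +/- 3 days from Study Visit 3"). Section 6.3 allows a short delay for intolerance: "Subjects can be rechallenged with cetuximab within 3 days but will otherwise be discontinued from the study". No passage sets a minimum gap between dose 2 and surgery. The Protocol Summary (Schematic of Study Design) says "There is no absolute timeframe for study procedures to occur, although all protocol activities must be completed prior to resection". The last pre-operative visit, "Study Visit 5, Safety Evaluation (within 7 days prior to surgery"), is tied to surgery and not to dose 2.

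**Measurement.** Section 8.2.3 says "The FFPE research and surgical specimens will be used to establish the change in Ki67". The post-treatment value is therefore taken on the day of resection, whenever that falls.

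**Analysis.** Section 12.4 (Analysis of Correlative Endpoints) states that the correlation between change in Ki67 and "putative biomarkers will be analyzed as a continuous variable and will be tested using" Pearson's coefficient. It plans the same coefficient for change in circulating tumor cells against change in Ki67. There is no covariate, stratification or sensitivity analysis for time since dosing.

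**Status.** These are exploratory endpoints 3.2.3.1 and 3.2.3.2. The sample size of 36 in Section 12.2 rests on clinical response by AXL group, and no power is claimed for Ki67.

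**The concern.** Section 2 describes Ki67 both as a surrogate for response and as a pharmacodynamic marker. A pharmacodynamic reading is normally interpreted relative to exposure. Here a specimen taken a day after dose 2 and one taken more than three weeks later enter the same correlation as if they were equivalent.

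Two things could follow. If the effect on Ki67 fades after the last dose, variation in the interval adds spread unrelated to AXL and shrinks the coefficient. If the interval is also related to AXL, part of any observed association would belong to timing. In either case a weak AXL-Ki67 result would be hard to read: it could mean that AXL does not matter, or that some specimens were taken late.

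**Working it through.** **1. Permitted interval.** Latest surgery is 4 × 7 = 28 days after dose 1. Dose 2 falls on day 7 − 3 = 4 to day 7 + 3 = 10.

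- Dose 2 on day 4: 28 − 4 = 24 days at most
- Dose 2 on day 7: 28 − 7 = 21 days
- Dose 2 on day 10: 28 − 10 = 18 days
- If the 3-day delay were added to day 10: 28 − 13 = 15 days

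No minimum is stated, so about 1 day is allowed.

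**2. The plan's own figures.** There is none for Ki67. For the primary endpoint, the unpooled normal approximation gives (1.645 + 1.282)² × (0.20 × 0.80 + 0.65 × 0.35/2) / 0.45² = 11.58, so 12 high and 24 low AXL, total 36. This reproduces the stated size but does not bear on the Ki67 question.

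**3. Model with measurement noise.** Nothing here comes from the documents except n = 36. Assume residual drug c = 2^(−t/h) at t days after dose 2, with half-life h of 3, 5 or 7 days; effect s = c/(c + 0.25); AXL standardised; change in Ki67 = (−20 + 7·AXL)·s(t)/s(7) + N(0, 12²). Tests are two-sided at 5%.

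With every patient at 7 days, r = 7/√(7² + 12²) = 0.50. Fisher's z gives power Φ(0.555 × √33 − 1.96) = 0.89; simulation gives 90%.

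Simulated power (runs differ by one or two points):

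| Interval | h = 3 | h = 5 | h = 7 |
|---|---|---|---|
| Fixed 7 days | 90% | 90% | 90% |
| Fixed 12.5 days | 28% | 62% | 75% |
| Uniform 1–24, unadjusted | 31% | 52% | 68% |
| Uniform 1–24, adjusted linearly | 45% | 62% | 72% |
| Uniform 7–14, unadjusted / adjusted | 48 / 51% | 73 / 74% | 82 / 81% |
| Uniform 10–18, unadjusted / adjusted | 20 / 19% | 50 / 50% | 68 / 69% |

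Mean unadjusted r for 1–24 days is 0.24, 0.33 and 0.39.

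**4. Splitting the loss.** A uniform 1–24 day gap has mean (1 + 24)/2 = 12.5 days, so comparing it with a fixed 7 days also moves sampling later. The fixed 12.5-day row has no variation to adjust for. At h = 5, s(12.5)/s(7) = 0.414/0.603 = 0.69, the slope is 7 × 0.69 = 4.8, and r = 4.8/√(4.8² + 12²) = 0.37. Later sampling alone accounts for the whole loss at h = 3, for 90 − 62 = 28 of 90 − 52 = 38 points at h = 5, and for 90 − 75 = 15 of 90 − 68 = 22 points at h = 7. Adjustment recovers 14, 10 and 4 points.

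**5. A different decay model.** Assume simple exponential fading, no assay noise, r = 0.50 without fading, and a uniform 1–24 day gap. The two figures in each range are for a between-patient SD of 0.5 and 1.0 times the mean effect.

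| Half-time of effect | Unadjusted r | Partial r |
|---|---|---|
| 4 days | 0.20–0.28 | 0.29–0.33 |
| 7 days | 0.29–0.37 | 0.40–0.42 |
| 14 days | 0.40–0.45 | 0.47 |
| 28 days | 0.47–0.49 | 0.49 |
| No fading | 0.50 | 0.50 |

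Without noise, late sampling costs nothing by construction, so adjustment recovers more here: at 4 and 7 days, power rises from 21–38% to 40–50% and from 40–61% to 68–71%.

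**6. Confounding.** Use the model in step 3 with no AXL effect, h = 5 and a 1–24 day gap. If AXL and the interval correlate at 0.2 or 0.4, the unadjusted false-positive rate is 8–9% or 19–21%, and about 5% after adjustment. With a 7–14 day gap the unadjusted rates are about 5% and 7%. If AXL and the interval are independent, there is no bias.

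**7. Cost of adjusting when nothing fades.** Power falls by about a point or less (89.8% to 89.3% in one run, 89.6% to 88.6% in another).

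**The case against.** The strongest reply is that the mechanism is not in the documents. Section 2 says Ki67 has served as a surrogate and pharmacodynamic marker; it gives no half-life, no concentration-effect relation and no recovery time. The range of 1 to 24 days is what the windows allow, not what scheduling will produce, and 24 days needs dose 2 on its earliest day. The background section links AXL to grade and distant metastases, but nothing links AXL to the date of surgery. The endpoints are exploratory. All of this stands, and it makes the conclusion conditional.

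A reader might infer that the fall from 90% power is the price of an unadjusted Pearson test. Step 4 shows otherwise: under that model most or all of the fall comes from later average sampling, which no analysis can recover. In that model the interval also multiplies the AXL slope, which a linear term does not restore.

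A reader might also extend the point to tumor shrinkage and ask for an adjusted primary analysis, or for an analysis restricted to early resections. The documents offer no basis for the first, and no calculation was made for it. The second would need a cutoff that nothing in the documents supplies.

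The objection does not remove the pooling of very different intervals in a marker that the protocol itself treats as pharmacodynamic, or the fact that adjustment is nearly free.

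**Conclusion.** The point holds in conditional form. The protocol permits resection about 1 to 24 days after dose 2, and Section 12.4 ignores the interval. Attenuation requires Ki67 suppression to fade materially within the window; confounding further requires the interval to be related to AXL. Neither is shown, so it would be wrong to say that wash-out does distort these correlations or that late-resected patients will look resistant.

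The size is unknown. Under the model with measurement noise, half-lives of 3 to 7 days and a uniform 1 to 24 day gap, linear adjustment adds roughly 4 to 15 points of power, and almost none for a 7 to 14 day spread. With slow or no fading there is little or nothing to correct. The simulations cover AXL only. Change in circulating tumor cells was not modelled; its pre-surgical blood is drawn within a day before surgery, so it shares nearly the same interval as Ki67. This is a cheap improvement to exploratory endpoints and does not touch the primary analysis.

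**What to change.** In Section 12.4, for endpoints 3.2.3.1 and 3.2.3.2, pre-specify a partial correlation (or the equivalent linear regression) of change in Ki67 with each biomarker, adjusted for days from dose 2 to resection. Report it beside the planned Pearson coefficient, not in place of it. Also report the distribution of that interval and its association with AXL, so that readers can judge whether attenuation or confounding is plausible in the data obtained.

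The cost is a few lines of analysis text and one degree of freedom in 36 patients. Dispensing dates (Section 6.4) and patient treatment calendars (Section 16) are already kept, and the surgery date should be in the medical record; confirm that both dates reach the analysis dataset. Surgical timing and the primary analysis stay as they are.
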